
2. Objectives

We hypothesize that the addition of an individually-tailored, multi-faceted environmental control strategy (ECS) to guidelines-based controller medication titration will result in less controller medication requirement and allergic inflammation than controller medication titration alone among urban asthmatic children. We will test this hypothesis and identify the factors that mediate the clinical effects of the ECS with a parallel-arm, randomized controlled trial of ECS plus controller medication titration vs. controller medication titration alone. The aims are:

- (1) To determine the effect of the addition of ECS to controller medication titration on controller medication requirements and allergic inflammatory biomarkers.
 - a) To compare the effect of the active intervention (“ECS+Medication Group”) to control (“Medication Group”) on controller medication requirement (“treatment step”) and inhaled corticosteroid dose.
 - b) To compare the effect of the active intervention to control on F_ENO, serum allergen-specific IgE levels.
- (2) To determine whether reductions in particulate matter (PM) and/or indoor allergens mediate the effects of an ECS on asthma.
 - a) To measure the change in fine and coarse particulate matter (PM_{2.5} and PM_{2.5-10}, respectively) and indoor allergen concentrations (cat, dog, mouse, cockroach, and dust mite) among study participants.
 - b) To estimate the causal effects of PM and allergen exposure reduction on controller medication requirements and allergic inflammatory outcomes, using a novel statistical approach, principal stratification analysis.
- (3) To evaluate whether a child’s personal bacterial exposures, particularly those of animal origin, contribute to asthma morbidity.
 - a) To compare bacterial community profiles and *S. aureus* genotypes in children versus pet and pest animals (dog, cat, mouse, cockroach others) in the home.
 - b) To examine associations between the child’s bacterial communities and asthma morbidity.
 - c) To determine relationships between the child’s *S. aureus* colonization and asthma morbidity.

3. Background

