Swabs for microbial assessment: The nares, oropharynx, and skin will be sampled using Copan E-swabs™ (Copan Diagnostics, Murrieta, CA) for staphylococcal culture and Catch-All™ sample collection swabs (Epicentre Biotechnologies, Madison, WI) for bacterial community analysis at CV1,2,3,and 4. The child may self-swab with the help of a parent/guardian.

At HVs: Home Assessment Visits (HV) will occur at baseline, 3 and 6 months. Home inspection, settled dust collection, PM₁₀, PM_{2.5}, airborne allergen measurements, and microbial air sampling may occur at all HVs. The air sampling of microbes and their products will be compared to dust samples collected. PM_{2.5-10} will be calculated, as done in previous studies, by subtracting the PM_{2.5} concentration from the PM₁₀ concentration that is measured adjacent to, and simultaneously with, the PM_{2.5} measurement. A passive filter for air nicotine monitoring will be placed in the home at baseline and 6 months.

Home inspection: A trained technician will conduct a home inspection to collect data regarding the home environment, including condition of dwelling, evidence of tobacco smoking, evidence of pets and pests.

Dust sample collection: Dust will be collected from the bed and bedroom floor using a standard procedure. The dust samples will be analyzed for the major relevant indoor allergens: Mus m 1, Der f 1, Fel d 1, Can f 1, and Bla g 1. A portion of the bedroom dust sample will be saved for future studies. A separate dust sample will be analyzed for bacterial communities and *S. aureus*, including staphylococcal enterotoxin proteins that may be secreted by the bacterium. Additional dust will be collected from standardized home surface sites using sterilized electrostatic cloths (autoclaved Swiffer™, Proctor & Gamble, Cincinnati, OH) for bacterial culture. Temperature and humidity data may also be collected.

If a participant moves between home visits, and the participant is randomized to receive intervention, an attempt will be made to collect another dust sample prior to the intervention visit.

URI Assessment: A respiratory illness questionnaire will be completed at the 3 month (HV2) home visit.

Socioeconomic Questionnaire: A questionnaire about specific socioeconomic factors will be administered at the first home visit.

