Bacterial Questionnaires: At the home visit we may collect data on established risk factors for acquisition of *S. aureus* and other bacteria, such as daycare, gym use, and antibiotic use, and household location (which will be collected on a separate form, then geocoded into X, Y coordinates from address data before linkage with health or demographic data).

Pet Questionnaire: We may collect data on participant contact with and characteristics of pet animals in the home. These data will include notations from visual inspection of the pets and areas of the house related to pets (e.g. pet crates).

Sampling of pets and pests: Under an approved ACUC protocol ([name], SP14H352, 9/18/2014-9/18/2017), Copan Eswabs™ (Copan Diagnostics, Murrieta, CA) for bacterial culture and Catch-All™ sample collection swabs (Epicentre Biotechnologies, Madison, WI) for bacterial community analysis may be collected from all pet animals at multiple anatomical sites and from freshly trapped rodents and other trapped pests. The informed consent process for these pet swabs will be conducted under the approved ACUC protocol and conducted by the [name] group. Study participants randomized to pest control will be given a magnet with a number to call to schedule optional pick-up of freshly trapped rodents and other pests from the home to transport to the laboratory for bacterial sampling.

Particulate Matter and Airborne Animal Allergens: Particulate matter monitoring will be conducted in the child's bedroom using integrated sampling direct-reading methods for an approximate 5 day period. Air samples for PM_{2.5} and PM₁₀ will be collected using methods developed during previous childhood asthma studies.⁽³⁴⁾ After gravimetric analysis, the PM₁₀ filters will be assayed for allergen content in the [name] laboratory. PM₁₀ samples will be analyzed because previous research indicates that the bulk of airborne animal allergens is contained on particles less than 10µm in aerodynamic diameter.^(35, 36) Microbial air sample measurements may be obtained.

Inspirotec air monitors will be deployed in a subset of homes to establish correlation between our PM10 measurements of airborne biomass and Inspirotec spectroscopic measurements of biomass. We will also compare the limits of detection of the two methods and validate the utility of the Inspirotec sampler as easily deployable in home environments.

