To evaluate the role of bacterial communities and *S. aureus* colonization on asthma morbidity, we will perform exploratory data analysis to identify outliers and missing data, and to generate descriptive summaries of multiple outcome variables related to asthma morbidity. The primary predictive variable will be *S. aureus* colonization. We will test *S. aureus* association with asthma outcomes over multiple visits using random effects models. In order to adjust for potential confounders, such as child demographic characteristics, *etc.*, we will construct multivariate random effects models that account for repeated assessment of the outcomes and time-varying covariates. For bacterial community analysis, we will compare taxonomical relative abundances using the Wilcoxon rank-sum test. Accounting for clustering within home and host, we will identify the influence of demographic and other factors on

microbial composition by calculating the weighted and unweighted UniFrac and the non-parametric ANOSIM (ANalysis of SIMilarities) test.

d. Early stopping rules.

The protocol may be halted by the DSMB, IRB or Sponsor upon review of SAEs.

7. Risks

a. Medical risks, listing all procedures, their major and minor risks and expected frequency.

Questionnaires

The risk of the questionnaire is breach of confidentiality.

Blood draw

The risk of blood drawing is discomfort, bruising, lightheadedness, and rarely infection.

Lung function and exhaled nitric oxide testing

The risk of lung function and eNO testing is the discomfort of exhaling forcefully, light-headedness and occasional minor chest soreness.

Home visits

The risk of the home visit for collection of environmental data is breach of confidentiality.

Skin testing

The risk of skin testing is primarily the discomfort from any positive skin tests, which would result in wheal and flare responses and pruritus. Approximately 2-3 in 10,000 skin prick tests results in allergic symptoms away from the site of the skin testing, such as sneezing, rhinorrhea, or rash.^(38, 39) Very rarely, an individual who experiences this type of reaction may develop life-threatening symptoms such as persistent coughing or wheezing. A study published in 1987 reported six fatalities from skin testing since 1945.⁽³⁹⁾ From 1985-1989 there were no fatalities from skin testing reported,⁽⁴⁰⁾ and one fatality was reported from 1990-2001.⁽⁴¹⁾

Buccal Cell Collection

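### The taxa comparison names an unpaired rank-sum test, and the plan's provision for home and host clustering is not extended to it

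*Combined protocol and SAP*

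**What the plan says.** The bacterial paragraph of the Analysis Plan (section 6c) names one test for individual taxa: "we will compare taxonomical relative abundances using the Wilcoxon rank-sum test". It does not say which groups are compared, at which visit or body site, or what the unit of analysis is.

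The next sentence opens "Accounting for clustering within home and host, we will identify the influence of demographic and other factors on" and continues "microbial composition by calculating the weighted and unweighted UniFrac and the non-parametric ANOSIM (ANalysis of SIMilarities) test". Home and host clustering is therefore recognised, but for the composition analysis. Earlier in the same paragraph, S. aureus is tested for "association with asthma outcomes over multiple visits using random effects models", with adjusted "multivariate random effects models that account for repeated assessment of the outcomes and time-varying covariates".

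The data have two kinds of dependence:

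- **Repeats within a child.** Section 3a (Swabs for microbial assessment) has children swabbed at the nares, oropharynx and skin "for bacterial community analysis at CV1,2,3,and 4".
- **Sharing within a home.** Aim 3a (section 2, Objectives) compares bacterial profiles "in children versus pet and pest animals (dog, cat, mouse, cockroach others) in the home". Section 3a (Sampling of pets and pests) says that swabs "may be collected from all pet animals at multiple anatomical sites". The visit schedule marks pet sampling at all three home visits, where there is a pet.

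**The concern.** The ordinary rank-sum test treats every value as independent of every other. Neither structure above meets that condition, and the two pull in opposite directions.

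A child and a pet from one home share exposures, and the Background section reports that pets increased bacterial sharing among household members. A positive correlation within homes makes the true variance of the child-animal difference smaller than the test assumes. The test is then conservative and misses real differences. Reducing each host to one value does not cure this, because the two hosts still share a home.

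Pooling repeated swabs from the same child does the reverse. It overstates the amount of independent information and yields too many false positive taxa.

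What is at stake is how the taxa-level results of Aim 3 can be read. The plan names no other test for individual taxa, and the paragraph states no multiplicity adjustment across taxa. Benjamini-Hochberg is stated only for the clinical and exposure outcomes.

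**Working it through.** The plan gives no sample size, power or error rate for Aim 3, so there is no figure of its own to reproduce.

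**Inputs from the documents:** 200 children; four swab visits; three body sites per child; pet sampling at up to three home visits.

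**Assumptions:** two-sided alpha of 0.05 (none is stated for Aim 3); two groups of 100 children; 60 homes with one child and one pet; correlations over a range, because the documents give none. Simulations use 4,000 runs each, so the Monte Carlo standard error near 0.05 is √(0.05 × 0.95 / 4,000) ≈ 0.003. The simulated values are continuous; taxa with many zeros are not modelled.

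**1. Child against pet in the same home, one value each.** With home correlation h, the variance of the difference in means is (1 − h) times what an independent-samples test assumes. The approximate actual error is 2[1 − Φ(1.96/√(1 − h))]. For h = 0.3, 1.96/√0.7 = 2.34, giving 0.019.

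| h | Formula | Rank-sum, simulated | Signed-rank, simulated |
|---|---|---|---|
| 0.1 | 0.039 | 0.036 | 0.044 |
| 0.3 | 0.019 | 0.022 | 0.049 |
| 0.5 | 0.006 | 0.009 | 0.059 |

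For a true shift of 0.4 SD with the same 60 pairs, the rank-sum test has power of about 0.58. The signed-rank test has about 0.72 at h = 0.3 and 0.85 at h = 0.5.

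**2. Between groups of children, four visits pooled.** With m values per child and within-child correlation ρ, the design effect is DE = 1 + (m − 1)ρ, and the actual error is 2[1 − Φ(1.96/√DE)]. For m = 4 and ρ = 0.3, DE = 1 + 3 × 0.3 = 1.9 and 1.96/√1.9 = 1.42, giving 0.155.

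| ρ | DE | Formula | Simulated |
|---|---|---|---|
| 0.2 | 1.6 | 0.121 | 0.117 |
| 0.3 | 1.9 | 0.155 | 0.150 |
| 0.5 | 2.5 | 0.215 | 0.211 |
| 0.7 | 3.1 | 0.266 | 0.252 |

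Pooling all 4 × 3 = 12 swabs would give 0.18 at ρ = 0.1 and 0.51 at ρ = 0.7 by the same formula. That treats all 12 as equally correlated, which is rough across body sites.

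**3. Between groups of children, one value per child.** Using a single visit, or each child's mean, simulated error is 0.042 to 0.051 at every correlation from 0 to 0.7. The test is valid here.

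**4. Both structures together.** Pooling four child and three pet swabs per home gives 0.024 with home correlation 0.3 and no further host correlation. It gives 0.122 with home correlation 0.1 and a further 0.3 within host. Even the direction of the error depends on correlations that are not known.

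**The case against.** The strongest reply is that this is missing detail, not a wrong method. The plan never says that visits are pooled, and step 3 shows that a rank-sum test on one value per child is sound. The paragraph opens with bacteria and asthma morbidity, which is Aims 3b and 3c, so applying the taxa test to the child-animal comparison is an inference; the clustered composition analysis could serve Aim 3a instead. Pet sampling is optional, and no number of pet homes is given. The authors plainly knew of the clustering, since they name it one sentence later.

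Much of this stands. Pooling is neither stated nor excluded, so the inflation in step 2 is conditional. The link to Aim 3a is inferred, although no other taxa test is offered for it. The reply fails in two respects. One value per host does not rescue the child-animal comparison (step 1). And even if the clustering clause was meant to reach back, an ordinary rank-sum test cannot account for clustering, so a different or modified test would still have to be named.

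A reader might infer that all Aim 3 p-values are wrong. The documents do not support that: the S. aureus analyses use random effects models for repeated assessments, and the composition analysis says that it accounts for home and host, although it does not say how.

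**Conclusion.** The point holds for one sentence of the plan. The taxa test assumes independence, and the clustering provision is not extended to it.

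For children against animals in the same home, the test is conservative even with one value per host: error of about 0.02 to 0.01 at home correlations of 0.3 to 0.5, with power of about 0.58 where a paired test has 0.72 to 0.85. With the four clinic visits pooled, error is about 0.12 to 0.26 at within-child correlations of 0.2 to 0.7. The correlations, the 60 pet homes and the 0.4 SD shift are assumptions, so these figures show the scale of the problem and do not predict this trial's error rates.

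Rank-sum comparisons between groups of children on one value each are valid. The S. aureus models, the UniFrac/ANOSIM analysis and the primary outcome are unaffected. The sentence should be amended before taxa results are seen, so that visit, site and pairing are not chosen with the data in view.

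**What to change.** Replace the rank-sum sentence in section 6c with wording such as:

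> Taxa relative abundances will be compared separately by body site. Child-animal comparisons, and comparisons that use repeated visits, will use mixed models on suitably transformed abundances with random effects for home and host. A rank-sum test will be used only for between-child comparisons with one value per child at a single pre-specified visit. P-values across taxa will be adjusted by Benjamini-Hochberg, as elsewhere in the plan.

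Averaging each host over sites and visits before a signed-rank test is a weaker option. It merges different habitats, mixes the visit at randomization with later visits in the intervention group, and does not form simple pairs in homes with several pets.

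The cost is slightly more analysis work, including the choice of a transformation, and fewer nominally significant taxa where visits would otherwise have been pooled. No new samples or visits are needed.

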(3) Microbial exposures: While bacterial exposures are known to influence the development of asthma, less is known about their impact on symptoms and lung function among children diagnosed with asthma. Further, it is not known whether the profile of bacterial exposures (e.g. in the nasal microbiome) or exposure to a single bacterium is important. A leading candidate bacterium is the Gram-positive *Staphylococcus aureus*, which colonizes a third of the U.S. population. *S. aureus* is known to exacerbate atopic eczema through its pro-inflammatory activity, primarily via a Th2, or allergic, immune response to bacterial superantigen proteins such as staphylococcal enterotoxins (SE). Emerging data indicate that *S. aureus* exacerbates upper respiratory disease via the same pathway, and there is evidence for a causal role of *S. aureus* in the development of chronic rhinosinusitis with nasal polyposis.⁽¹⁹⁾ A number of limited but provocative studies suggest that *S. aureus* may also exacerbate asthma;^(20, 21) and our study using NHANES data demonstrates that *S. aureus* colonization is an independent risk factor for current asthma and emergency department (ED) visits for asthma among children and young adults. Our pilot work demonstrates that the presence of pet and pest animals in the household contribute to bacterial exposures and may modify risk for colonization with *S. aureus*. Presence of pest mice in urban households was associated with a two-fold increased likelihood of environmental *S. aureus* contamination. In a controlled trial of people with *S. aureus* infection, we identified both pet carriage and presence of pests in the home as risk factors for human *S. aureus* colonization, and we found that pets generally enhanced bacterial sharing among household members.

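### ANOSIM, the plan's only test of overall bacterial-community composition, takes no continuous or multiple covariates and reacts to unequal spread, so its result cannot be read as a composition shift

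*Combined protocol and SAP*

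**What the plan says.** The statistics for Aim 3 are one paragraph of the Analysis Plan (section 6.c).

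- **S. aureus.** "The primary predictive variable will be" *S. aureus* colonization, related to asthma outcomes over several visits by random effects models. For confounders, "we will construct multivariate random effects models that account for repeated assessment of the outcomes and time-varying covariates".
- **Bacterial communities.** Relative abundances of taxa are compared with the Wilcoxon rank-sum test. Overall composition is then covered by one sentence. It begins "Accounting for clustering within home and host, we will identify the influence of demographic and other factors on" and continues "microbial composition by calculating the weighted and unweighted UniFrac and the non-parametric ANOSIM (ANalysis of SIMilarities) test".

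The paragraph names no covariates for the community analysis, no test of equal dispersion and no method for handling the clustering. Section 2 (Objectives) states Aim 3b as "To examine associations between the child’s bacterial communities and asthma morbidity". The Analysis Plan assigns no adjusted community-versus-morbidity model to that aim.

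**The concern.** The sentence sets out to separate the influence of several factors, some of them continuous (age runs from 5 to 17 years). ANOSIM compares ranked between-group and within-group distances for one grouping. It does not estimate one factor adjusted for others, and it does not separate a difference in average composition from a difference in variability.

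Two misreadings follow. A significant result may be reported as a community shift when one group is only more variable, or when the groups differ on a confounder. A null result may hide a real shift when the larger group is the more variable one. The community swabs are taken at four clinic visits (CV1 to CV4), so a fair amount of data rests on this one test.

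**Working it through.** **The plan's own figure.** There is none. The documents state no power, group sizes, spread or error rate for Aim 3. I use 200 children (the trial's sample size) and assume a 5% level. Everything else below is assumed.

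**Why spread alone moves the statistic.** ANOSIM uses R = (mean between-group rank − mean within-group rank) / [n(n−1)/4]. For insight, take squared Euclidean distances per axis with identical centroids and SDs s1 and s0. The expected within-group values are 2·s1² and 2·s0², and the expected between-group value is s1² + s0². Let s1 = 1.3 and s0 = 1, giving 3.38, 2.00 and 2.69.

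- *67/133, smaller group more variable.* Within-group pairs: 67×66/2 = 2,211 and 133×132/2 = 8,778, total 10,989. Mean within = (2,211×3.38 + 8,778×2.00)/10,989 = 2.28, below 2.69. R is pushed up.
- *67/133, larger group more variable.* Mean within = (8,778×3.38 + 2,211×2.00)/10,989 = 3.10, above 2.69. R is pushed down, so a real shift has to overcome a negative bias.
- *100/100.* Mean within = (3.38 + 2.00)/2 = 2.69, equal to the between value. Squared distances balance here, but ranks do not. Simulated mean R was 0.03 to 0.15 at SD ratios of 1.25 to 2, small but enough to reject.

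PERMANOVA works on squared distances. With identical centroids, its expected between-group mean square over its within-group mean square is:

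- 100/100: 1.345/1.345 = 1.00.
- 67/133, smaller group more variable: [(133×1.69 + 67)/200] / [(66×1.69 + 132)/198] = 1.459/1.230 = 1.19.
- 67/133, larger group more variable: [(67×1.69 + 133)/200] / [(132×1.69 + 66)/198] = 1.231/1.460 = 0.84.

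It is affected in the same direction when sizes and spread both differ, but not when sizes are equal.

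**Simulated rejection rates, identical centroids, nominal 5%** (10 axes, 199 permutations for ANOSIM):

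| Groups | SD ratio | ANOSIM | PERMANOVA |
|---|---|---|---|
| 100/100 | 1.0 | 6.5% | 6.0% |
| 100/100 | 1.25 | 98.3% | 4.0% |
| 100/100 | 1.3 | 100% | about 5% |
| 67/133, smaller more variable | 1.3 | 100% | about 8% (10% in another run) |
| 67/133, larger more variable | 1.3 | 0% | about 1% |
| 60/140, smaller more variable | 1.25; 1.5 | 100%; 100% | 13.5%; 16.8% |
| 60/140, larger more variable | 1.25; 1.5 | 0%; 0% | 1.5%; 0.3% |

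If only 3 of the 10 axes are more variable (ratio 1.3), ANOSIM rejects 33% with 100/100 and 81% with 67/133.

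**Distances closer to UniFrac.** A further run used sequence counts, 40 taxa, equal mean composition and weighted-UniFrac-type distances on a random tree. ANOSIM rejected 2% to 3.5% with equal spread. With within-group distances about 1.14 times larger in one group it rejected 45% to 52% (100/100) and 92.5% (67/133, smaller more variable). At about 1.3 times it rejected 100% in both layouts. It rejected 0% when the larger group was more variable. PERMANOVA rejected 6% to 13% at 1.14 and 35% to 56% at 1.3.

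**Confounding, no true group effect.** A binary confounder, present so that 65% versus 35% fall in the index group, shifts every axis by 0.3, 0.5 or 1.0 SD:

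| Test | 0.3 | 0.5 | 1.0 |
|---|---|---|---|
| ANOSIM, unadjusted | 12.7% | 39.7% | 90.0% |
| PERMANOVA, unadjusted | 22.7% | 50.7% | 90.7% |
| ANOSIM, permuted within strata | 2.7% | 5.3% | 6.3% |
| PERMANOVA, permuted within strata | 5.0% | 6.0% | 4.7% |

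Adjustment is what matters here. The choice of test matters because PERMANOVA accepts continuous and multiple covariates.

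**Clustering.** With 100 children, four visits, within-child correlation 0.5 and visits permuted as if independent, ANOSIM rejected 76% and PERMANOVA 68%. Neither test works without a permutation scheme that respects the clustering.

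**The case against.** *The sentence does not name asthma morbidity.* A reader might infer that Aim 3b will report a false community shift. The documents do not support that. They assign ANOSIM to the influence of demographic and other characteristics on composition, and the home-and-host wording could equally fit the child-versus-animal comparison of Aim 3a. What stands is conditional: if ANOSIM is used for Aim 3b, the problem carries over; if it is not, Aim 3b has no adjusted community analysis.

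*ANOSIM can be adjusted.* For a categorical confounder, yes: permuting within strata restored the level. The plan does not specify this. It does not practically extend to continuous or several covariates, and it does not remove the sensitivity to spread.

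*The 100% rates reflect the set-up.* This is largely right. They need all axes inflated; with 3 of 10 the rate falls to 33% in equal groups. A one-third to two-thirds split might be drawn from the Background's statement about *S. aureus*, "which colonizes a third of the U.S. population", but that is a US carriage figure and the plan does not name carriage as an ANOSIM grouping. Here 67/133 only illustrates imbalance, which is not required: equal groups are affected too.

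*PERMANOVA is not immune.* Correct, and in the count-based run it was far from nominal. It is recommended only together with the dispersion test.

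*The aim is peripheral.* Also correct. Aim 3 lies outside the primary and listed secondary outcomes, and its main exposure, *S. aureus*, already has adjusted repeated-measures models.

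**Conclusion.** The point holds as a minor one. As the plan stands, a significant ANOSIM cannot be read as a difference in average composition, and a null result does not exclude one. At an SD ratio of 1.3 in 200 children, rejection under identical centroids ranged from 0% to 100% depending on which group was more variable and on how many axes, against a nominal 5%.

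These rates rest on assumed spread, group sizes, confounding and mostly Euclidean data. They show direction and possible size, not the error rate this trial will have. The structural findings need no simulation: the plan names one overall-composition test, gives it no covariates and no dispersion check, and specifies no adjusted community-versus-morbidity model for Aim 3b. The randomized comparison and the trial's main conclusion are unaffected.

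**What to change.** In section 6.c, replace ANOSIM with PERMANOVA on the same weighted and unweighted UniFrac distances, and state four things:

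1. The covariates, fixed in advance from data the protocol already provides for, such as age, sex, season, antibiotic use and pets. The protocol says that antibiotic and pet data may be collected, and at home visits rather than with the clinic swabs, so add a rule for matching dates and for missing values.
2. A permutation scheme that respects clustering within home and host, including the repeated visits.
3. A test of equal dispersion beside every result. A composition shift is claimed only when unequal dispersion does not explain the finding.
4. That the same adjusted model is used for community versus asthma morbidity (Aim 3b).

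The cost is a few lines of text and slightly more analysis, with the same samples, the same distances and standard software. The remaining weakness is that PERMANOVA can be liberal or conservative when spread differs, especially with unequal group sizes. The dispersion test flags this but does not cure it.
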